**I. Specific Aims:**

- a) To perform a comparative trial of the “Total Capture” hysteroscopy drape (TCD) versus the standard drape during patient surgeries to document improved, real-time determination of patient fluid absorption. Inaccurate detection of fluid absorption by a patient during hysteroscopy is a source of complications, morbidity and mortality from excessive patient fluid absorption. Pilot testing of a prototype design of the “Total Capture” drape versus the conventional hysteroscopy drape indicated remarkable improvement in fluid capture and accurate fluid deficit determination in a plastic pelvic model experiment. The interest from corporate producers of hysteroscopy fluid management systems and drape manufacturers is contingent upon demonstrating “proof of concept” with actual patient surgeries.
  
- b) To evaluate the clinical usefulness of the TCD compared to the Standard drape for hysteroscopy with the standardized metrics of: 1) the Human Factors Surgical Drape Assessment and 2) The System Usability Scale. These metrics will allow us to quantitate clinical usefulness and usability of both the operating surgeons and operating room staff.

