#### **Measures for Drape Usability, Quality, and Convenience**

We plan to objectively and subjectively evaluate the usability and usefulness of the TCD compared to the standard drape. Staff will be asked to complete the System Usability Scale (SUS) [section XVII SUS; Brooke, 1986] to evaluate their perceived clinical usefulness of the TCD and the standard drape. The SUS is a validated 10-item survey for assessing perceived usability that uses a 5-point Likert scale ranging from strongly disagree to strongly agree. To further subjectively and objectively assess the TCD a human factors and design researcher will observe the surgeries. The human factors researcher will attend the first surgeries to ensure consistent rating with design researcher who will subsequently observe the remaining surgeries until data saturation is reached. The human factors expert will attend any surgeries the design researcher cannot attend. Staff will be asked to speak aloud using the system, which the researcher will record. Further, the researcher will complete an objective human factors assessment tool (section XVII). Finally, enrolled surgeons will be provided the opportunity to participate in one-on-one feedback sessions or focus group sessions to provide suggestions on how they perceive usability of the drape can be improved. These sessions will be facilitated by the Principal Investigator and the design researcher or human factors expert. These metrics will allow us to quantitate clinical usefulness and usability of both the operating surgeons and operating room staff. These results will not only provide this assessment of the TCD compared to the standard hysteroscopy drape (which is used across ORs within CHS) but will also provide important information to improve the drape if deficiencies are identified.

Adverse events and serious adverse events will be captured along with relatedness and severity. We will classify event terms using Common Terminology Classification of Adverse Events version 4.03 (National Cancer Institute).

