## **VI. Randomization and Blinding**

We will use standard randomization to allocate patients in a 1:1 allocation to the TCD or the standard hysteroscopy drape. The randomization lists will be generated by a study statistician within [name] team using SAS Enterprise Guide version 6.1. The assignments will be opaque envelopes which ensure allocation

concealment. Once a patient consents and is deemed eligible for the study, the study coordinator will provide the next envelope to the operation nurse who will open the envelope in privacy to learn the allocation. All study staff collecting and recording data for the trial will be masked to the drape that was used during the procedure.

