Assessment Tool for the surgeons and operating team members. Once data saturation is reached using the Human Factors Assessment Tool, enrolled surgeons will be provided a step-by-step video link orientation to the Total Capture Drape. For the SUS, we will collect data on attending physicians only on their first and fifth procedures (the study team may change it to 1st and 3rd if deemed appropriate). We will estimate means or medians with standard deviations (or interquartile ranges) for the items and total scores for the SUS. Both within (1st vs. 5th) and between arms (TCD vs. standard) comparison on total scores of SUS will be conducted. We will compare the two groups using linear mixed models or generalized linear mixed models (depending on the distribution) with a random effect for the procedure to control for correlation of the measures among team members participating in the same procedure.

At this early stage of investigation, we have no prior data on HFD in patients to estimate the variability need for the sample size estimation. We have preliminary data from the simulated experiment showing a 100% recovering of loss deficit by the TCD. If we conservatively assume the loss deficit will decrease from 40% to 20% of the inflow volume, this would result in a clinically meaningful improvement with an approximate effect size of 0.92 based on the variability of loss deficit in the simulation. Given this, we are using effect size (relative to standard deviation) as the primary justification for the number of patients needed for the study. With a sample size of n=34 per arm, we would have 81% power to detect an effect size of 0.7 (0.7\*standard deviation of the HFD) with a two sided, two sample t-test ( $\alpha=0.05$ ). To account for potential missing data of 10%, we propose randomizing 76 women (n=38 per arm). With n=34 women in each group, we would also have 80% power to detect an absolute 33% reduction in the proportion of procedures with the alarm sounding due to fluid deficit threshold being reached assuming the proportion in the standard drape arm is 50%. This power was calculated using a Fisher's Exact test for testing proportions between two independent samples. The same power would apply for detecting differences in the proportion of procedures terminated.

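### The SUS model names a random effect for procedure only, so repeat ratings by the same surgeon are left uncorrelated; the main cost is lost precision for the first-versus-fifth comparison

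*Combined protocol and SAP*

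**What the plan says.** On the SUS, section VIII states: "For the SUS, we will collect data on attending physicians only on their first and fifth procedures", with leave to use the first and third instead. It plans a first-versus-fifth comparison, and says a "between arms (TCD vs. standard) comparison on total scores of SUS will be conducted".

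One sentence gives the method. It opens: "We will compare the two groups using linear mixed models or generalized linear mixed models (depending on the distribution"). The correlation structure is then limited to a single term, worded as follows: "with a random effect for the procedure to control for correlation of the measures among team members participating in the same procedure". No surgeon or rater effect, occasion term or paired test is named for the SUS. Surgeon is adjusted for in the primary model for hysteroscopy fluid deficit (HFD), where section VIII calls it a stratification factor, but this is not carried over to the SUS.

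The documents differ on who rates. Section VIII points to attendings. The subsection on drape usability measures says "Staff will be asked to complete the System Usability Scale (SUS"), and aim (b) in section I wants the metrics to "quantitate clinical usefulness and usability of both the operating surgeons and operating room staff".

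Allocation is by patient: "We will use standard randomization to allocate patients in a 1:1 allocation to the TCD or the standard hysteroscopy drape" (section VI).

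**The concern.** The schedule makes the same surgeon rate more than once, and usability scores from one person tend to resemble each other. The random effect that is named addresses a different correlation, that between people in the same room, which does not arise if attendings alone rate. So the model covers a dependence that may be absent and omits the one that the schedule creates.

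At stake is the precision of one of the two metrics named in aim (b), in a small data set. A within-surgeon contrast analysed as if the ratings were independent has too large a standard error. A drape contrast can go either way, depending on how a surgeon's two ratings fall across the drapes.

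**Working it through.** The documents give no SUS sample size, standard deviation, power or within-surgeon correlation, so there is no SUS figure to reproduce. The number of surgeons and the correlation rho are assumptions below. Total variance is set to 1, attendings alone rate, and tests are two-sided at 0.05.

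**1. What the procedure effect does with one rating per procedure.** Write rating = fixed effects + u(procedure) + e. Each row has variance var(u) + var(e), and any two rows have covariance 0. Only the sum of the two variances is identified. In a 20-row example the log-likelihood was -33.66 at every split tried. The term therefore absorbs no correlation, and the fit is ordinary least squares.

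**2. First versus fifth, complete pairs.** With J surgeons, the variance of the mean difference is 2(1 - rho)/J; the procedure-only model takes it as 2/J. The ratio of model to true standard error is 1/sqrt(1 - rho):

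- rho 0.3: 1/sqrt(0.7) = 1.20
- rho 0.5: 1/sqrt(0.5) = 1.41
- rho 0.7: 1/sqrt(0.3) = 1.83

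Simulation with 12 surgeons gives type I error of about 2%, 1% and 0.2%, so the test is conservative. For an assumed change of 0.8 SD and 12 complete pairs, power is 44/43/43% without a surgeon effect and 53/66/87% with one. With 10 pairs it is 38/36/35% and 48/62/83%.

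**3. Incomplete pairs.** Of 76 procedures, at most 15 surgeons can reach a fifth (76/5 = 15.2). With the 76 spread unevenly over 8, 10 or 15 surgeons and counted overall, about 6.0, 6.6 and 7.0 surgeons reach it. The step 2 ratio then falls as follows:

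| Surgeons | rho 0.3 | rho 0.5 | rho 0.7 |
|---|---|---|---|
| 8 | 1.14 | 1.27 | 1.48 |
| 10 | 1.14 | 1.26 | 1.44 |
| 15 | 1.11 | 1.21 | 1.32 |

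**4. Drape contrast.** Let k of J surgeons have the same drape at both ratings, with balanced arms of J ratings each. A same-drape surgeon contributes variance 2(1 + rho) to the signed sum and a mixed-drape surgeon 2(1 - rho). The true variance is [2k(1 + rho) + 2(J - k)(1 - rho)]/J² = (2/J)[1 + rho(2k/J - 1)], against 2/J in the model. The ratio is 1/sqrt(1 + rho(2k/J - 1)). For J = 12 this formula gives the ratios below; type I error is simulated with drape and occasion in the model. Simulated ratios agree with the formula to within about 0.02.

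| k of 12 | SE ratio, rho 0.3/0.5/0.7 | Type I error |
|---|---|---|
| 4 | 1.05/1.10/1.14 | about 4/3/2% |
| 6 | 1.00/1.00/1.00 | about 5% |
| 8 | 0.95/0.93/0.90 | about 6/7/8% |
| 9 | 0.93/0.89/0.86 | about 7/8/9% |

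Averaged over the uneven allocations of step 3, the drape ratio is 1.00 (0.996 to 1.005) and type I error is 5%.

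**5. How likely most surgeons are to have the same drape twice.** With independent 1:1 draws, the binomial probability of 8 or more of 12 is 19%, and of 9 or more 7%. If the list is blocked within surgeon, the chance per surgeon is at most one half. For first and fifth inside one block of 6 it is 2/5, and 8 or more of 12 has probability 5.7%. For first and third in a block of 4 it is 1/3, and the probability is 1.9%. For first and fifth with blocks of 4 the draws fall in different blocks and 19% stands.

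**The case against.** The strongest objection is that the harm runs mostly in the safe direction. The first-versus-fifth error is conservative in every case computed, and it arises only if the procedure-only model is used there. The method sentence speaks of comparing two groups, which most naturally means the arms, so the analyst might simply use a paired test. That stands as a limit on size. It does not settle the matter, because neither a pairing nor an occasion term is written down.

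A reader might infer that the drape comparison will produce false positives. The documents do not support that. Patients are randomized, so drape is random at each rating and type I error averages about 5%. Section VIII names surgeon as a stratification factor. The block size is not stated, and strata also split by indication would weaken the effect, but blocking within surgeon can only make repeated same-drape pairs less likely. If occasions are counted within drape, the drape contrast is mostly within surgeon. Simulation with 8, 10 or 15 surgeons and blocks of 4 then gives type I error of 0.4 to 2.9%: lost power instead.

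A reader might also infer that the procedure effect is simply wrong. If staff rate as well, it is needed; what is missing is the rater.

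The planned within comparison may mean within each arm. A model that pools occasions over drapes would then change it, and the fix allows for this.

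Finally, the SUS is in neither list of secondary outcomes (Clinical Study Design; section VIII) and has no power claim. That stands, and it keeps the point minor.

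**Conclusion.** The point holds as a minor one. The SUS model omits the correlation that its own rating schedule creates, whoever rates; if attendings alone rate, the one random effect named does nothing in the linear model.

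The main consequence is lost precision for within-surgeon contrasts: a standard error up to 1.20 to 1.83 times too large for first versus fifth at rho 0.3 to 0.7 with complete pairs, and about 1.1 to 1.5 times with realistic incomplete ones. Excess false positives for drape, about 6 to 8% at 8 of 12 same-drape pairs, are a chance outcome and not the expected one.

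Surgeon number, case distribution, correlation and the 0.8 SD change are all assumed. The drape table and power figures use complete pairs, which is more than 76 cases would probably give. Only the usability aim is affected; the primary HFD analysis is not.

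**What to change.** In section VIII, replace the procedure-only random effect for SUS totals with a random intercept for the rater (the surgeon, if attendings only), plus fixed effects for drape and occasion. Use this model for both the between-drape and the first-versus-fifth comparison. Add a drape-by-occasion term if first versus fifth is meant within each arm. Keep a procedure effect, crossed with rater, only if several people rate the same procedure. If a generalized linear mixed model is used, include the same rater effect.

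For the linear model name a small-sample correction such as Kenward-Roger. With 12 complete pairs it held type I error at 4.7 to 5.7% for drape and 4.9 to 5.6% for occasion. Satterthwaite degrees of freedom without the standard-error correction gave 6.3 to 7.6% for drape at 6, 8 or 9 same-drape pairs. Neither was checked with fewer pairs.

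As supporting wording, reconcile section I, the usability subsection and section VIII on who completes the SUS, and state whether occasions are counted overall or within drape. Within-drape counting would leave few later ratings: with 8, 10 or 15 surgeons, on average only 2.5, 2.1 and 1.2 would reach a fifth procedure with both drapes.

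The model change costs a few degrees of freedom and needs no new data. Settling who rates and how occasions are counted could affect which forms are collected, so it is best done before ratings begin.

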Loss of uncollected distention medium onto the floor and into operating room blankets creates other hazards to the patient and surgical team besides the significant patient risks of fluid absorption. Fluid standing on the operating room floor can pose a fall risk to surgical team members (7). The effluent fluid from the patient that is not collected contains blood and bodily fluids that expose the surgical team to the hazards of infectious disease and biological toxins. Significantly, fluid becomes an electrical hazard when it comes into contact with electrical equipment. Distention medium that escapes capture may come in contact with electrical outlets, switches, and surgical electrodes increasing the risk of burns, fires and damage to equipment.

Additionally, the inaccurate detection of the fluid deficit may pose a clinical dilemma for the hysteroscopic surgeon. Does the surgeon stop a procedure when the fluid management alarm indicates that a fluid deficit (approximate patient fluid absorption) exceeds the safe limit even though they see fluid on the floor? If the surgery proceeds, how long can it safely continue? Without accurate, real-time fluid absorption data, surgeries may be prematurely terminated because of erroneously reported high fluid deficits thus requiring a potentially unnecessary repeat surgery with a delay in cure, increased cost, and more patient risks. The surgical team and healthcare system would certainly be exposed to medico-legal risk if a fluid management alarm sounds, the procedure is continued and the patient suffers a complication of fluid overload.

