### **III. Guideline Recommendations for Fluid management During Hysteroscopy**

Use of an automated fluid pump and monitoring system is advocated by both the American College of Obstetricians and Gynecologists and the American Association of Gynecologic Laparoscopists (8, 9). Guidelines for the threshold for acceptable fluid absorption by patients during hysteroscopy have been established by these groups. Most guidelines indicate that a threshold for safe absorption by patients is 500 to 750 mL for non-electrolytic media and 1000 mL for electrolytic medium such as normal saline. Data indicate that fluid absorption of greater than 1000 mL of electrolytic medium is associated with an increased risk of gas embolism (10). It has been shown with routine postoperative CT imaging of the brain that cerebral edema can occur with as little as 500 mL of non-electrolytic distension solutions (1). For other patients with cardiovascular disease or other comorbidities, the threshold for

safe absorption of medium should be reduced. An alarm can be set to sound a warning when a preset volume deficit is reached. Most operating rooms mandate a halt to the procedure following a warning alarm and, in some cases, special post-operative patient monitoring is required for patients to insure fluid and electrolyte normality, adequate pulmonary function, and hemodynamic stability.

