### Clinical Study Design

---

The primary outcome variable for the comparative trial will be the hysteroscopy fluid deficit (HFD) which can be precisely measured by the fluid management system by subtracting the outflow volume (OV) returned to the fluid management system from the inflow volume (IV). That is:

$$HFD = IV - OV$$

Secondary outcomes include uncollected fluid volume (UFV), occurrence of the alarm sounding for exceeding the fluid deficit limit, and procedure interruption. The UFV is defined as the difference of HFD between TCD and standard drape group. The UFV will be two components as determined by the circulating OR nurse in charge of the fluid management system. The first are the volume on the floor and the volume absorbed by the operation blankets and drapes. The second component is an estimate of any fluid loss from leaking hysteroscopy joints and gaskets not captured by the collection bag. In addition, the time required for procedures will be recorded.

Adverse events and serious adverse events will be captured along with relatedness and severity. We will classify event terms using Common Terminology Classification of Adverse Events version 4.03 (National Cancer Institute).

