## VIII. Statistical Methods and Sample Size Justification

The primary outcome for the study is the hysteroscopy fluid deficit (HFD) as determined by the fluid management system by subtracting the outflow volume (OV) from the inflow volume (IV) ( $HFD = IV - OV$ ). Our null hypothesis is  $H_0: \mu_{Standard} = \mu_{TCD}$  where  $\mu$ =mean fluid deficit. Our alternative hypothesis is  $H_a: \mu_{Standard} > \mu_{TCD}$  due to the underestimation of the outflow volume created by the loss of outflow fluid to floors and blankets. If we assume the true absorption rates by the patients are the same between the groups due to randomization, by estimating and testing the difference HFD between the two groups we are estimating and testing a more accurate measure of the uncollected fluid volume (UFV) as shown below:

$$\begin{aligned} \mu_{Standard} - \mu_{TCD} &= (\mu_{Standard, \text{true absorption}} + \mu_{Standard, \text{UFV}}) - \mu_{TCD, \text{true absorption}} \\ &= (\mu_{\text{true absorption}} + \mu_{Standard, \text{UFV}}) - \mu_{\text{true absorption}} \\ &= \mu_{Standard, \text{UFV}} \end{aligned}$$

The primary analysis for the study will use a general linear model on the HFD with a fixed effect for study group (TCD versus Standard drape) controlling for surgeon and indication for hysteroscopy, the stratification factors for the randomization.

Secondary outcomes include estimated uncollected fluid volume from floor and blankets, occurrence of the fluid deficit alarm sounding, stopping of the operation due to concerns of overabsorption by the patient, and adverse events. Estimated uncollected fluid volume will be analyzed similar to the primary outcome. All other outcomes are categorical and will be compared using Chi-square analyses.

We will sample 10 procedures (or until data saturation) from each arm (TCD vs standard) to conduct qualitative assessments on Usability using the Human Factors

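### Does the stopping outcome change meaning between sections, and is its power claim left without a basis?

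*Combined protocol and SAP*

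**What the plan says.** Clinical Study Design lists among the secondary outcomes "occurrence of the alarm sounding for exceeding the fluid deficit limit, and procedure interruption". No cause is given there, and nothing says whether the interruption must be permanent.

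Section VIII (Statistical Methods and Sample Size Justification) gives the corresponding item as "stopping of the operation due to concerns of overabsorption by the patient". Two sentences later it sets the test: "All other outcomes are categorical and will be compared using Chi-square analyses".

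The sample size paragraph of section VIII says of the alarm: "With n=34 women in each group, we would also have 80% power to detect an absolute 33% reduction in the proportion of procedures", with 50% assumed in the standard arm and Fisher's exact test as the method. It then adds: "The same power would apply for detecting differences in the proportion of procedures terminated".

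Two background statements bear on the meaning. Section II warns that "surgeries may be prematurely terminated because of erroneously reported high fluid deficits thus requiring a potentially unnecessary repeat surgery". Section III says: "Most operating rooms mandate a halt to the procedure following a warning alarm".

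**The concern.** The three labels can be read as different events. They could differ on two points: whether the procedure is paused or ended, and whether any reason counts or only worry about absorbed fluid. A procedure halted after an alarm and later completed is an interruption but not a termination, and it is unclear whether it is a stop. A procedure ended for an unrelated reason would fit the first and third labels but not the second.

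If the event were open, the result could depend on a choice made after the counts are known. The power sentence also looks unsupported, because the 80% was derived from inputs stated for the alarm only. Avoiding needless stops is one of the protocol's own arguments for the new drape, so the outcome has some weight even though it is secondary.

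**Working it through.** **1. Which event is tested.** Setting the sections side by side:

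| Place | Label | Cause stated | Test stated |
|---|---|---|---|
| Clinical Study Design | interruption | no | no |
| VIII, analysis text | stopping | yes, overabsorption concern | chi-square |
| VIII, power paragraph | terminated | not in that sentence, which follows the deficit-alarm sentences | Fisher, for power |

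The analysis text names the event and its test together, so the tested event is fixed as a stop for overabsorption concern. The two lists also run in parallel: uncollected fluid, then alarm, then this item. Section II asks whether a surgeon should stop when the deficit alarm sounds, contrasts that with carrying on, and then speaks of termination caused by falsely high deficits. Stop and terminate therefore describe one scenario there, with the same cause. The looser word is *interruption*, a short label in the design section.

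**2. The plan's own power figure.** Inputs from section VIII: n = 34 per arm, p_S = 0.50, p_T = 0.50 − 0.33 = 0.17, Fisher's exact test. Two-sided α = 0.05 is stated for the t-test and is assumed here to apply to proportions too. Exact power is

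Power = Σₓ Σᵧ Bin(x; 34, p_S) · Bin(y; 34, p_T) · 1[p-value(x, y) ≤ 0.05].

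- 0.50 vs 0.17: Fisher 77.9%, uncorrected chi-square 85.3%.
- 0.50 vs 0.167 (33% read as one third): Fisher 78.9%, chi-square 86.2%.

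The stated 80% is reproduced to within rounding of the inputs. If terminations share these inputs, the carried-over sentence is arithmetically true.

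**3. If terminations have other rates.** The documents give none, so every rate below is an assumption (n = 34 per arm, two-sided 0.05).

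| Standard → TCD | Basis | Fisher | Chi-square |
|---|---|---|---|
| 45% → 12% | 33-point fall kept | 82% | 89% |
| 40% → 7% | 33-point fall kept | 88% | 93% |
| 30% → 3.4% | larger relative fall (26.6/30 = 89%) | 81% | 90% |
| 40% → 13.6% | alarm's relative fall kept (33/50 = 66%) | 61% | 73% |
| 30% → 10.2% | same 66% | 43% | 56% |
| 20% → 6.8% | same 66% | 23% | 38% |

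The results fall on both sides of 80%. Below a standard-arm rate of 33%, a 33-point fall is impossible, so the sentence cannot be inheriting the alarm difference there.

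**4. Could the definition alter a result?** With assumed counts out of 34 and z = (difference in proportions) / √[p̄(1 − p̄)·2/34]:

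- 17 vs 6: difference 11/34 = 0.324, p̄ = 23/68, z = 2.82, p = 0.005.
- 9 vs 3: difference 6/34 = 0.176, p̄ = 12/68, z = 1.91, p = 0.056.
- 9 vs 2: difference 7/34 = 0.206, p̄ = 11/68, z = 2.31, p = 0.021.

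A stricter count could move the p-value across 0.05. But the last two lines differ by one patient and also fall on opposite sides of 0.05, so the example shows the fragility of small counts as much as any effect of definition.

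**The case for a change.** The strongest case for a change is that no section defines any of the three labels or says that they are the same. Section III says that most, not all, operating rooms require a halt after an alarm, and a halt may be a pause or an end. Section II presents stopping or continuing as a real dilemma for the surgeon, so the stopping rate need not equal the alarm rate. Section VII mentions forms for the procedure and surgical outcomes, but the forms are not in the documents, so nothing shows that pause and end are recorded separately. The remedy would cost a few words and no patients.

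Part of this stands. Whether a procedure paused and then completed counts as stopped is not written down, and neither is the rate assumption behind the carried-over power.

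The wider claim does not stand. The event for the chi-square test is named, with its cause. Reading the power sentence as covering stops for unrelated reasons means taking it out of a paragraph about deficit alarms. No section denies what another asserts: a short label, a full description and a one-word reference are not a contradiction. The absence of the forms from the documents is also no evidence that the distinction goes unrecorded.

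**Conclusion.** No change to the plan follows. This is loose naming of one secondary outcome, plus a power sentence that leaves its inputs implicit, and an analyst would fill both sensibly. The analysis text of section VIII governs: the event is a stop for overabsorption concern, compared by chi-square. Whether a resumed procedure counts is a data-definition detail that can be settled when the case report forms are built.

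No figure is shown to be wrong. The alarm power is 78% to 79% by Fisher against a stated 80%, and 85% to 86% by the planned chi-square test. For terminations, the assumed rates above give 23% to 88% (Fisher) or 38% to 93% (chi-square), so no shortfall is established. The primary outcome is unaffected, and so is the sample size, which rests on the effect size for the fluid deficit.

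This conclusion assumes that the power sentence inherits the alarm inputs it follows, and that two-sided α = 0.05 applies to the proportions. A documented termination rate well below 50%, without a correspondingly larger relative reduction, would make the power sentence too optimistic. Even then, no design decision depends on it.
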